supported. The app will be selected from a limited set of well-established options such as LoseIt!, MyFitnessPal, Apple Health, or Google Fit. The PGHD requested through active tracking and patient data entry will include self-monitoring elements previously shown to be successful at encouraging obesity-related behavioral change (129), such as calorie intake, food logging, minutes of physical activity, and weight. Patient contextual data requested through passive tracking may include items such as geographic location, sleep quality, and heart rate. Any additional data requested will be determined based on the results of Aim 1 and in consultation with the research team to identify social, behavioral, and clinically relevant information. Both intervention and control patients will be weighed on a clinic scale and asked to complete three PROMs pre- and post-intervention. These include the short form of the Patient Activation Measure (PAM-13), which is a validated PROM that assesses an individual's knowledge, skills and confidence in self-management behaviors (35, 36); the HRQOL-4, which is a validated PROM that assesses patients' overall physical and mental health status over the prior 30 days (37); and the Healthy Days Symptoms Module, which is a validated PROM that assesses physical and mental health symptoms which may have affected patients' lives over the prior 30 days (37). Intervention patients will also be asked to complete the three PROMs once each per month over the course of the 16-week intervention by email, online web form, text message, or app-based private message. Only privately submitted PROM data will be used in analysis, to protect patient privacy and to avoid social desirability bias due to self-curation behaviors associated with public reporting. One PROM will be collected per week, to avoid overburdening patients while ensuring a monthly collection of PROM data. The fourth week will include a simple check-in request, to maintain the weekly communication pattern. PGHD and PROs data will be extracted from shared systems, online forms, and messages as appropriate and placed into a REDCap (130) research database created for the project. These data will also be made available to and actionable by DH providers monthly through manual transfer to practice-standard patient-reported data forms and subsequent entry into the EHR. As this is a feasibility study, automated data exchange is beyond the scope of this initial project; however, the product of Specific Aim 3 will support future automated integration.

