
Outcomes and measures. The primary outcome of interest for the RCT is *patient engagement*. This outcome will be measured by patient response rates to data requests; by the frequency of unprompted messages sent by patients to research personnel; and by performance on the PAM-13. Secondary outcomes include weight loss and performance on the HRQOL-4 and Healthy Days Symptoms PROMs pre- and post-intervention. Weight loss will be assessed as change in body mass index (BMI) and absolute percent weight.

Data Analysis. Descriptive statistics will be computed for participant demographic characteristics (e.g., age, gender, race/ethnicity). Group differences (intervention vs. control) will be evaluated to ensure that the random group assignments were similar. If statistically significant differences ($p < 0.05$) are found between the groups for demographic or baseline measures, these will be controlled for in subsequent analyses. Logistic regression or the Chi-square test of proportions will be used to test differences in response rates and PROM scores between the RCT intervention and control groups. The distribution of the number of unprompted messages will be assessed and either analyzed using Poisson regression or dichotomized based on a clinically relevant cut-off and analyzed with either logistic regression or the Chi-square test of Proportions. Weight loss will be analyzed using the most appropriate and parsimonious multivariable regression technique, based on the nature of the outcome variable (e.g., continuous, time-varying, dichotomous, etc.). Fuzzy-set QCA will be conducted to examine the impact of factors identified through work conducted under Specific Aim 1.

Power. A total sample size of 256 patients is necessary to detect a proportional difference of 20% (0.55 intervention; 0.40 control) in the primary outcome between the intervention and control groups with 90% power ($\alpha = 0.05$). A sample size of 192 patients would be needed at 80% power. Given the nature of this feasibility study, we will attempt to recruit 300 patients for the RCT, but will consider the study adequately powered with 200 patients enrolled (100 intervention, 100 control). This also allows for some loss to follow-up.

3.4.3. Specific Aim 3. To create an ontology mapping and set of interoperability resources which can be used to support integration of PGHD and PROs into clinical information systems.

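### Weight loss: adjust for the baseline value whatever the baseline test shows, and fix a continuous clinic-scale comparison, since both arms have only one such weight before and one after

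*Combined protocol and SAP*

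**What the plan says.** All references are to the combined protocol and SAP, section 3.4.2.

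- **Role.** Outcomes and measures: "Secondary outcomes include weight loss and performance on the HRQOL-4 and Healthy Days Symptoms PROMs pre- and post-intervention". The primary outcome is patient engagement.
- **Metric.** Same paragraph: "Weight loss will be assessed as change in body mass index (BMI) and absolute percent weight". Neither metric is ranked above the other, and no responder cut-off for weight is given.
- **Measurement.** Methods: "Both intervention and control patients will be weighed on a clinic scale and asked to complete three PROMs pre- and post-intervention". Between those two weighings, weight tracking by app or fitness tracker is requested of intervention patients only.
- **Model.** Data Analysis: "Weight loss will be analyzed using the most appropriate and parsimonious multivariable regression technique, based on the nature of the outcome variable". The examples of that nature are "e.g., continuous, time-varying, dichotomous, etc".
- **Baseline covariates.** Data Analysis: significant differences at p < 0.05 that "are found between the groups for demographic or baseline measures, these will be controlled for in subsequent analyses". No covariate is named as always included.

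**The concern.** Two features of the plan can be improved with what it already collects.

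First, a significance test on baseline data decides whether baseline weight enters the model. In a properly randomised trial any baseline difference is due to chance, so the test says nothing useful about whether the covariate is worth having. What matters is whether baseline weight predicts the outcome, and that can be judged in advance.

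Second, the list of possible outcome forms is wider than the data support. One clinic weight before and one after, with the outcome defined as change, gives a continuous pre-post outcome. A dichotomous form would discard information. A time-varying form, if it drew on app-logged weights, would use interim values that exist in the intervention arm alone, come from a different source and depend on who chose to log.

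At stake is the precision and comparability of the main clinical measure in a weight-management trial. The primary outcome and the sample size are not affected.

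**Working it through.** The plan gives no SD, effect size or power for weight loss, so there is no figure of its own to reproduce. The totals in its Power paragraph concern engagement. Only one input is taken from there: 100 patients per arm, the size it accepts as adequate. Everything marked as assumed below is not in the documents.

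**1. How often the rule admits baseline weight.** With valid randomisation, a test at p < 0.05 is positive in about 5% of trials. Baseline weight is therefore included on that ground in about 1 trial in 20 and left out in 1 − 0.05 = 0.95, or 19 in 20.

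**2. What leaving it out costs for a change outcome.** Let ρ be the correlation between pre and post weight, with equal variance at both times. Per unit of weight variance, the change score has variance 2(1 − ρ) and the baseline-adjusted analysis has 1 − ρ². The ratio is 2/(1 + ρ). Set the adjusted analysis to 80% power at 100 per arm (two-sided α = 0.05, assumed effect):

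| ρ (assumed) | Variance ratio | Power, unadjusted change |
|---|---|---|
| 0.80 | 1.111 | 76% |
| 0.90 | 1.053 | 78% |
| 0.95 | 1.026 | 79% |
| 0.99 | 1.005 | 79.8% |

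The rule itself was simulated: 4,000 trials per setting, 100 per arm, BMI 25.0 to 39.9 as in the eligibility range. Assumed were an SD of weight change of 4 kg, an effect of 0 or 1.6 kg, and a slope of change on baseline weight of 0, −0.03 or −0.10.

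- Mean estimate under the rule: −1.59 to −1.62 kg against a true −1.6 kg, so no bias.
- Type I error: 4 to 5%.
- Power: 76 to 80% under the rule, against 79 to 81% with baseline always included. At the steepest slope it was 76.0% against 80.9%, a loss of 4.9 points.

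**3. What dichotomising would cost if it were used.** The relative efficiency of a normal outcome split at proportion p is φ(z)²/[p(1 − p)].

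- p = 0.5: 0.637, so 200 patients carry the information of 200 × 0.637 = 127.
- p = 0.2: 0.490, so 200 × 0.490 = 98.

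In terms of power, the standardised effect that gives 80% at 100 per arm is (1.960 + 0.842) × √(2/100) = 0.396. Shifting the responder rate by that amount gives:

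| Control responder rate (assumed) | Intervention rate | Power at 100 per arm | N per arm for 80% |
|---|---|---|---|
| 50% | 65.4% | 60% | 161 |
| 20% | 32.8% | 54% | 185 |
| 10% | 18.8% | 43% | 249 |
| 5% | 10.6% | 31% | 360 |

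**4. Time-varying form.** No arithmetic applies. Methods gives both arms two clinic weights and asks only intervention patients to track weight in between. A model fed with the tracked values has repeated data in one arm and none in the other, so its interim contrast is not a randomised comparison.

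**The case against.** The strongest reply is that the plan already points to the right analysis. It defines weight loss as change in two naturally continuous metrics and ties the technique to the type of variable. Its list of types is a set of examples, and no cut-off for weight appears anywhere. This largely stands: the dichotomising figures describe an analysis that the plan allows but does not schedule.

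A reader might infer that the form will be picked after the data are seen. The text does not say so. Where the authors mean to look first, for unprompted messages, they say that the distribution will be assessed; the weight sentence has no such wording. Simulated reporting of the best of six analyses raised type I error to 10–12%, but two of the six used cut-offs (3% and 5%) that are absent from the documents. With the two named metrics kept continuous it was 5–6%.

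Two further replies have some force. The plan never says that covariates failing the baseline test are excluded, and it calls the regression multivariable, so including baseline weight is compatible with the text. But no covariate is guaranteed, and the test is the only inclusion rule given. Also, a repeated-measures model of the two clinic weights would treat weight as time-varying and still be like-for-like; the difficulty arises only if app-logged weights enter.

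Finally, the outcome is secondary and unpowered in a feasibility study. That limits the consequence, but it is no reason to forgo a free gain.

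**Conclusion.** The point holds as a modest improvement. The baseline-test rule is a weaker method than always adjusting: it would omit a potentially prognostic covariate in about 19 trials of 20, at a cost of about 0 to 5 power points for a change outcome. That range rests on the assumed SD, effect and slope; it shrinks towards zero as change becomes unrelated to baseline weight.

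A reader might also infer that the rule biases the comparison. It does not: the simulated estimates centre on the true effect and type I error stays at 4 to 5%. A large loss without adjustment would need a comparison of unadjusted final weights (23% power at ρ = 0.9), which the plan does not propose.

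The open list of forms matters only if a weaker form is used. Dichotomising would then cost about 20 power points or more under the assumed effect, and a model using app-logged weights would lose the like-for-like comparison. Neither is stated as the intention. Both can be ruled out in a sentence.

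**What to change.** In section 3.4.2, Data Analysis, replace the weight-loss sentence with wording to this effect:

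- Percent change in weight and change in BMI, from clinic-scale measurements before and after the 16-week programme, are each analysed as continuous outcomes by linear regression on arm.
- The baseline value (weight or BMI respectively) is always included, whatever the baseline comparison shows.
- Results are adjusted mean differences with 95% confidence intervals.
- Only clinic-scale weights enter the between-arm comparison; app-logged weights are described within the intervention arm.
- Any responder cut-off is reported descriptively.

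State also that the percent-weight metric means percent change from baseline, if that is the intention. Both metrics are already named; whether to rank one above the other is the sponsor's choice and this point does not depend on it.

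The cost is a few lines of text. Baseline weight and BMI are already collected, so no new data, visits or patients are needed.

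### The power statement contradicts itself: 0.55 vs 0.40 is a 15-point difference, not 20%, and 256 and 192 patients do not give 90% and 80% power at those rates

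*Combined protocol and SAP*

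**What the plan says.** The sample-size justification is one paragraph in section 3.4.2 (Specific Aim 2, Power). It says: "A total sample size of 256 patients is necessary to detect a proportional difference of 20% (0.55 intervention; 0.40 control) in the primary outcome", at 90% power and alpha 0.05. It continues: "A sample size of 192 patients would be needed at 80% power". On recruitment, "we will attempt to recruit 300 patients for the RCT", but the team "will consider the study adequately powered with 200 patients enrolled (100 intervention, 100 control". The paragraph ends: "This also allows for some loss to follow-up".

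The paragraph does not say whether the test is one- or two-sided, and it gives no expected loss rate. The Data Analysis paragraph of the same section names logistic regression or a chi-square test for comparing response rates. No other section supplies event rates or explains the 20%.

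**The concern.** One sentence gives a difference and two rates that do not match: 0.55 minus 0.40 is 0.15. An error in the difference, in one rate or in the totals would each have a different consequence, so the totals have to be recomputed to see which printed figures belong together.

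The plan draws a decision from this calculation, namely that 200 enrolled patients are enough. If a 20-point difference was meant, that holds narrowly before any loss. If the printed rates were meant, the trial falls well short of 80% power at 200, and a null result on engagement could be read as evidence from an adequately powered trial when it was not.

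**Working it through.** **Inputs, all from the Power paragraph of section 3.4.2:** rates 0.55 and 0.40; stated difference 20%; alpha 0.05; total 256 for 90% power and 192 for 80%; floor 200 (100 per arm, so 1:1); target 300. **Assumption:** two-sided test, since the plan does not say. One-sided results are also given.

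**Step 1. The difference.**
- Absolute: 0.55 − 0.40 = 0.15.
- Relative to control: 0.15/0.40 = 37.5%.
- Relative to intervention: 0.15/0.55 = 27.3%.

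None is 20%.

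**Step 2. Sample size at the printed rates.** Pooled two-proportion formula, per arm, with p̄ the mean of the two rates and d their difference:

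n = [z(α/2)·√(2p̄(1−p̄)) + z(β)·√(p₁(1−p₁) + p₂(1−p₂))]² / d²

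For 0.55 vs 0.40: p̄ = 0.475, √(2 × 0.475 × 0.525) = 0.7062, √(0.2475 + 0.2400) = 0.6982, d² = 0.0225.
- 80%: (1.960 × 0.7062 + 0.8416 × 0.6982)²/0.0225 = 172.8 per arm, total 345.6, so **346**.
- 90%: (1.960 × 0.7062 + 1.2816 × 0.6982)²/0.0225 = 230.8 per arm, total 461.7, so **462**.

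The plan's 192 and 256 are not reproduced.

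**Step 3. Other methods at 0.55 vs 0.40** (totals for 80% / 90%):

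| Method | Two-sided | One-sided |
|---|---|---|
| Pooled | 346 / 462 | 272 / 376 |
| Continuity-corrected | 372 / 488 | 300 / 404 |
| Unpooled | 342 / 456 | 268 / 372 |
| Arcsine | 346 / 464 | 274 / 378 |

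None comes near 192 / 256. Reading 192 and 256 as per-arm numbers gives two-sided power of 84.0% and 92.7%, and it contradicts the plan's description of 256 as a total. Taking 20% as a relative change moves further away: 0.48 vs 0.40 needs 1,208 / 1,614, and 0.55 vs 0.44 needs 648 / 866 (pooled, two-sided).

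**Step 4. Rates that do fit.** For 0.55 vs 0.35: p̄ = 0.45, √(0.495) = 0.7036, √(0.475) = 0.6892, d² = 0.04.
- 80%: (1.960 × 0.7036 + 0.8416 × 0.6892)²/0.04 = 95.94 per arm, total 191.9, so **192**.
- 90%: (1.960 × 0.7036 + 1.2816 × 0.6892)²/0.04 = 127.94 per arm, total 255.9, so **256**.

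Both stated totals are reproduced exactly. By the same formula 0.65 vs 0.45 also gives exactly 192 / 256, though both printed rates would then be wrong, and 0.60 vs 0.40 gives 194 / 260. The ratio of the stated totals, 256/192 = 1.33, also points to a two-sided test: one-sided totals at the printed rates have ratio 376/272 = 1.38.

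**Step 5. Power at the plan's sample sizes.** Power = Φ{[d√n − 1.960·√(2p̄(1−p̄))] / √(p₁(1−p₁) + p₂(1−p₂))}, two-sided, n per arm. For example, 0.55 vs 0.40 with n = 100: (1.500 − 1.384)/0.698 = 0.166, and Φ(0.166) = 0.566.

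| Rates | N = 192 | 200 | 256 | 300 |
|---|---|---|---|---|
| 0.55 vs 0.40 (printed) | 54.9% | 56.6% | 67.3% | 74.2% |
| 0.55 vs 0.35 | 80.0% | 81.6% | 90.0% | 94.0% |
| 0.60 vs 0.40 | 79.6% | 81.2% | 89.7% | 93.8% |

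Exact enumeration of the uncorrected chi-square test agrees to about 2 points (printed rates: 55.4%, 58.6%, 68.1%, 75.9%). One-sided at the printed rates, power is 68.6% at 200 and 83.3% at 300.

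**Step 6. Loss to follow-up.** On the favourable reading (0.55 vs 0.35), the tolerable loss is:
- from 200 to 192: 8/200 = 4.0%;
- from 300 to 256: 44/300 = 14.7%;
- from 300 to 192: 108/300 = 36.0%.

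With an assumed loss of 10% to 20%, two-sided power is:

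| Enrolled | 0.55 vs 0.35 | 0.55 vs 0.40 |
|---|---|---|
| 200 | 77% to 72% | 52% to 48% |
| 300 | 91% to 88% | 70% to 65% |

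**The case against.** The best reply is that three printed items agree with one another: the 20%, the 256 and the 192. A single wrong digit in the control rate (0.40 for 0.35) explains everything, while the damaging reading requires the difference and both totals to be wrong. This is also a feasibility study, and it aims for 300, where the favourable reading has ample room for loss.

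Much of this stands. A misprint is the likelier explanation, and the remark about loss to follow-up holds at 300. It does not settle the matter, because more than one pair of rates fits the totals and the document does not confirm any of them. The feasibility label does not help either, since the plan itself claims a specific power and declares 200 adequate.

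Two qualifications also stand. The power figures assume a two-sided test; a one-sided test at the printed rates would pass 80% at 300 but not at 200, and would still not reproduce 192 or 256. They also describe one binary comparison, whereas the plan measures engagement in three ways (response rates, unprompted messages and the PAM-13), so they are not the power of the trial as a whole.

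**Conclusion.** The concern holds. As printed, the rates, the difference and the totals cannot all be right, and this does not depend on the choice of formula or on sidedness. The consequence depends on what was intended:

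- **20-point difference intended:** a rate is misprinted and the totals stand. Two-sided power is 81–82% at 200 evaluable patients and 94% at 300. The floor of 200 has only 4% room for loss before power drops below 80%.
- **0.55 vs 0.40 intended:** the stated power is too high. Two-sided power is about 57% at 200, 67% at 256 and 74% at 300, so neither the floor nor the target reaches 80%.

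The exact match at 0.55 vs 0.35 favours the first reading but does not prove it. The results assume 1:1 allocation and a two-sided 5% test; the 10–20% loss range is an assumption. Because the plan's claim of adequacy at 200 rests on this paragraph, it must be corrected. The narrow allowance for loss at 200 is a secondary point.

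**What to change.** The sponsor should state which rates were intended and rewrite the paragraph so that rates, difference, sample size and power agree, with the sidedness of the test given.

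- If a 20-point difference was intended, print the correct pair and call it 20 percentage points. With 0.55 vs 0.35 the totals 192 and 256 stay; with 0.60 vs 0.40 they become 194 and 260.
- If 0.55 vs 0.40 was intended, print 15 percentage points, give 346 and 462 as the two-sided requirements for 80% and 90% power, and restate power as about 57% at 200, 67% at 256 and 74% at 300.
- If another pair was intended, recompute every figure from it.

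In each case, express the floor of 200 in evaluable patients, or state the power it gives after a named expected loss.

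The cost is the wording and figures of one paragraph. Design and enrolment do not change. If the printed rates were the intended ones, the plan will have to report a less favourable power.

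### The floor of 200 enrolled patients leaves only 8 (4%) above the plan's own 192 for 80% power, so calling it adequately powered with room for loss to follow-up is wrong as written

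*Combined protocol and SAP*

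**What the plan says.** The Power paragraph of section 3.4.2 (Specific Aim 2) makes four statements.

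- **90% power:** "A total sample size of 256 patients is necessary to detect a proportional difference of 20" per cent, with the rates given as 0.55 (intervention) and 0.40 (control) and alpha 0.05. Sidedness is not stated.
- **80% power:** "A sample size of 192 patients would be needed at 80% power".
- **Recruitment:** the team will try to recruit 300, but "will consider the study adequately powered with 200 patients enrolled (100 intervention, 100 control").
- **Loss:** the paragraph closes with "This also allows for some loss to follow-up".

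No attrition rate, inflation formula or count of analysed patients appears in the text available for this check (the text between sections 3.1 and 3.3 was not). The same section describes a 16-week programme, with the PAM-13 and two other questionnaires completed before and after it. It defines the primary outcome, engagement, by three measures: response rates to data requests, frequency of unprompted messages, and the PAM-13.

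**The concern.** A power requirement concerns patients in the analysis, whereas the plan's minimum is expressed in patients enrolled. The two figures, 192 and 200, lie so close together that the minimum has almost no reserve, yet the next sentence tells the reader that loss has been allowed for.

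If recruitment stops at the floor, the analysed sample for any measure that needs follow-up drops below the plan's own 80% requirement after the ninth loss. A report could still cite the protocol's statement that the study was adequately powered. A null result on engagement would then be read with more confidence than the design supports.

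**Working it through.** **Inputs (section 3.4.2).** Alpha 0.05; 1:1 allocation; totals of 192 (80%) and 256 (90%); rates 0.55 and 0.40, described as a 20% difference; floor 200; target 300. Two-sided testing is assumed. Loss rates of 5 to 20% are assumed, for illustration only.

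**Formulas.** Pooled two-proportion normal approximation, with p̄ the mean of the two rates, m the number per arm and Δ = p1 − p2:

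- Total N = 2 × [1.960·√(2p̄(1 − p̄)) + z_power·√(p1(1 − p1) + p2(1 − p2))]² / Δ²
- Power = Φ{[Δ√m − 1.960·√(2p̄(1 − p̄))] / √(p1(1 − p1) + p2(1 − p2))}

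**Step 1: reproduce the plan's totals.**

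| Rates | N for 80% | N for 90% |
|---|---|---|
| Plan states | 192 | 256 |
| 0.55 vs 0.35 (20 points) | 191.9 | 255.9 |
| 0.55 vs 0.40 (as printed) | 345.6 | 461.7 |

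The totals match a 20-point difference, not the printed pair, which is 15 points apart. One-sided testing does not rescue the printed pair (272 and 376), nor does a continuity correction (372 and 488).

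**Step 2: margin at the floor, taking 192 at face value.** 200 − 192 = 8, and 8/200 = 4.0%. For the target, 1 − 192/300 = 36%.

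**Step 3: power at the floor.** For 0.55 vs 0.35 with m = 100, p̄ = 0.45: (0.20 × 10 − 1.960 × 0.7036)/0.6892 = 0.901, so power is 81.6%. For 0.55 vs 0.40, p̄ = 0.475: (0.15 × 10 − 1.960 × 0.7062)/0.6982 = 0.166, so power is 56.6%.

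| Assumed loss | Analysed of 200 | Power, 0.55 vs 0.35 | Power, 0.55 vs 0.40 | Enrolment that keeps 192, 192/(1 − d) |
|---|---|---|---|---|
| 0% | 200 | 81.6% | 56.6% | 192 |
| 4% | 192 | 80.0% | 54.9% | 200 |
| 5% | 190 | 79.6% | 54.4% | 203 |
| 10% | 180 | 77.4% | 52.2% | 214 |
| 15% | 170 | 75.0% | 49.9% | 226 |
| 20% | 160 | 72.4% | 47.6% | 240 |

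**Step 4: the target.** With 300 analysed, power is 94.0% for 0.55 vs 0.35 and 74.2% for 0.55 vs 0.40.

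**The case against.** Five things can be said for the plan.

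1. **Eight patients is some loss, and the plan never says that 200 enrolled gives 80% power after loss.** True of the words. But the only benchmarks it gives for adequacy are 80% and 90%, and the floor meets the lower one only if loss stays within 4%.
2. **The closing sentence may refer to the target of 300.** This is possible, since target and floor stand in the same sentence, and for 300 the statement is sound on the 20-point reading. However, the floor is called adequate on either reading, and a reader cannot tell which number carries the allowance.
3. **Dropouts need not leave every primary measure.** This stands in part. A silent patient can be scored as a non-responder for response rates and as sending no messages. A missing post-intervention PAM-13 cannot be recovered that way, and the plan does not say how dropouts are counted.
4. **It is a feasibility study.** It still makes explicit power claims for a between-group test, so those claims should be accurate.
5. **The mismatch between 20% and the printed rates is the larger defect.** Agreed. But if a 20-point difference was intended, 192 and 200 both stand, and the thin margin remains.

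A reader might go further and infer that 80% power cannot be delivered at any realistic attrition. The documents do not support that. They give no attrition rate by which to judge what is realistic, and the decline is gradual: 79.6% at 5% loss is a trivial shortfall.

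**Conclusion.** Wrong as written, for the floor of 200 only. On the plan's own 192 the reserve is 8 patients. On the 20-point reading, power drops below 80% once more than 4% are lost from the analysis, and the deficit is roughly 3 to 8 percentage points at assumed losses of 10 to 20%. On the printed rates no reserve exists: about 57% power at 200 and about 74% at 300, both before any loss.

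This rests on two-sided testing at 0.05, equal arms, and losses that remove patients from the analysis. It applies to the post-intervention PAM-13, and to response rates only if dropouts are excluded rather than counted as non-responders. The target of 300 is not at fault on the 20-point reading.

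**What to change.** 1. First reconcile "a proportional difference of 20% (0.55 intervention; 0.40 control") so that the difference and the two rates agree, and state the sidedness of the test.
2. Replace the statements that 200 enrolled is adequate and that loss is allowed for with a requirement in analysed patients. On the 20-point reading: *80% power requires 192 patients in the analysis; with an assumed loss of d, 192/(1 − d) patients will be enrolled.* State d and the reason for choosing it.
3. Report the power if only 200 are enrolled, over a range of d, as in the table above.
4. Say how dropouts are counted for each of the three primary measures.
5. Keep the recruitment target of 300. If the printed rates turn out to be the intended ones, recompute everything and state the power that 300 gives (about 74% before loss).

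**Cost.** The stated power at the floor becomes less favourable, and on the 20-point reading the enrolment that secures 192 rises above 200 (214 to 240 at 10 to 20% loss). That stays within the existing target of 300, so no additional recruitment is needed beyond what is already planned.
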